### 9.2.4 Adverse Events

Adverse events will be recorded during each visit (Visits 1, 2, 3, 4, 5, and 6) and at other visits caused by postponement of treatment or incomplete treatment.

All medical events, whether observed by the Investigator or reported by the subject, and whether or not thought to be treatment-related, will be considered AEs and recorded on the appropriate AE form.

#### Adverse Event Definition

An AE is defined as any untoward medical occurrence in a clinical study, in which a subject is administered a medicinal product that does not necessarily have a causal relationship with this treatment. An AE can therefore be any unfavorable and unintended sign (including an abnormal laboratory finding), symptom, or disease temporally associated with the use of a medicinal (investigational) product, whether or not it is related to the medicinal (investigational) product. This includes an exacerbation of pre-existing conditions or events, intercurrent illnesses, drug interaction, or the significant worsening of the indication under investigation, that is not recorded elsewhere in the eCRF under specific efficacy assessments.

Note(s):

- Any new sign or symptom reported by the subject that appears after accidental or intentional overdose or misuse should be reported as an AE.
- Whenever possible, a diagnosis should be reported on the AE form, instead of signs, symptoms, or abnormal laboratory values.
- Pregnancy is not to be considered an AE; however, it must be monitored and reported as described in [Section 9.2.4.4](#).
- Each new episode of a chronic disease (e.g., hay fever, allergy) from the screening visit should be reported as a new AE.

The Investigator or designee will report all AEs that occur from the time the ICF is signed until the end of the study. The sponsor/CRO should be informed if the Investigator becomes aware of any safety information that appears to be drug related, even after the subject has completed the clinical study.

At each post-enrollment visit, the Investigator (or sub-investigator) will question the subject about his/her experiencing of AEs, using an open non-persuasive question to elicit reporting of AEs (for example, “Have you noticed any change in your health since the last visit?”). Directed questioning and examination will then be performed as appropriate.

Any AE occurring during the AE reporting period, whether it is related to the study drug(s) or not, will be recorded immediately in the source document and described on the Adverse Event Form (“AE Form”) along with the date of onset, severity, relationship to the study drug(s), and outcome, without omitting any requested and known information. Additional information will be requested under certain circumstances.

Adverse events assessed as related to the treatment or study procedure will be monitored until they have resolved or reached a stable condition. Other AEs will be monitored until the last visit if they have not resolved or reached a stable condition.

The Investigator will obtain and maintain all pertinent medical records in the subject’s files, information and medical judgment from colleagues who assisted in the treatment, and follow-up of the subject. If necessary, the Investigator will contact the subject’s personal physician or hospital staff to obtain further details.

### Assessment of Severity

Each AE will be assigned a category by the Investigator as follows:

- |           |  |
|-----------|--|
| Mild:     | An AE that is easily tolerated by the subject, causes minimal discomfort, and does not interfere with everyday activities. |
| Moderate: | An AE that is sufficiently discomforting to interfere with normal everyday activities; intervention may be needed.         |
| Severe:   | An AE that prevents normal everyday activities; treatment or other intervention usually needed.                            |

If there is a change in severity of an AE, it must be recorded as a separate event.

---

## Assessment of Causality

The Investigator is to determine whether there is a reasonable causal relationship between the occurrence of the AE, and exposure to the study drug (i.e., MAL cream or vehicle cream) and/or study procedure (e.g., illumination, blood sample collection). Medical judgment should be used to determine the relationship, considering all relevant factors including the pattern of the reaction, temporal relationships, relevant medical history, and confounding factors such as co-medication or concurrent diseases.

The expression “reasonable causal relationship” is meant to convey in general that there are facts or arguments to suggest a causal relationship (ICH E2A, Section IIIA 1).

The relationship assessment for an AE is to be completed using the following definitions as a guideline for all AEs occurring during this clinical study:

### Reasonable possibility:

According to the reporting Investigator, there is a reasonable possibility (i.e., suggestive evidence or arguments) that there is a causal relationship irrespective of the dose administered:

- Between the study drug (methyl aminolevulinolate hydrochloride 16.8% cream or vehicle cream) and the AE, and/or
- Between the clinical study protocol procedure (e.g., topical background therapy, blood sample collection) and the AE

### No Reasonable Possibility:

No suggestive evidence or arguments can be identified regarding a causal relationship between the study drug or the clinical study protocol procedure and the AE.

### Action Taken with Study Drug

The investigator will describe the action taken with study drug due to the adverse event in the appropriate section of the eCRF, as follows:

- Dose Not Changed
- Drug Interrupted – cream applied, no DL exposure, then removed
- Drug Withdrawn – cream not applied

### Other Action Taken

The investigator will describe the other actions taken (i.e. the ones not related to the study drug) in the appropriate section of the eCRF, as follows:

- None

- 
- Concomitant medication (any additions or discontinuations)
  - Other, specify

### Follow-up of Adverse Events

All Investigators should follow-up with subjects with related AEs until the event is resolved or until, in the opinion of the Investigator, the event is stabilized or determined to be chronic. Details of AE resolution must be documented in the eCRF.

Subjects should be followed up for 12 weeks ( $\pm$  5 days) after receiving the last dose of study drug, and any AEs that occur during this time should be reported according to the procedures outlined above.

### Documentation and Reporting of Adverse Events

Adverse events should be reported and documented in accordance with the procedures outlined below. All AEs occurring during the study must be documented on the relevant eCRF pages. The following data should be documented for each AE:

- Description of the symptom/event
- Classification of “serious” or “not serious”
- Severity
- Date of first occurrence and date of resolution (if applicable)
- Action taken with study drug
- Other action taken
- Causal relationship
- Outcome of event (unknown, recovered, not yet recovered, recovered with sequelae, death [with date and cause reported])

#### 9.2.4.1 Serious Adverse Events

An SAE is any untoward medical occurrence or effect that, at any dose,

- Results in death.
- Is life-threatening (an AE is life-threatening if the subject was at immediate risk of death from the event as it occurred, i.e., it includes a reaction that might have caused death if it had occurred in a more serious form).
- Requires or prolongs inpatient hospitalization. (Complications occurring during hospitalization are AEs and SAEs, if they cause prolongation of the current hospitalization. Inpatient hospitalization is considered to have occurred if the subject has had to stay for a night at the hospital. The criterion for prolongation of hospitalization is also defined as an extra night at the hospital. Hospitalization may not constitute sufficient grounds to be considered as an SAE, if it is solely for the purpose of diagnostic tests [even if related to an AE], elective hospitalization for an intervention that was already planned before subject enrollment in the clinical study, admission to a day care facility, social admission [e.g., if the subject has no place to sleep], or administrative admission [e.g., for a yearly

---

examination]. The details of such hospitalizations must be recorded on the medical history or physical examination eCRF.)

- Results in persistent or significant disability/incapacity. (An AE is incapacitating or disabling if it results in a substantial and/or permanent disruption of the subject's ability to carry out normal life functions.)
- Results in a congenital anomaly/birth defect.
- An important medical event that may not result in death, be life-threatening, or require hospitalization, may be considered an SAE when, based upon appropriate medical judgment, the event may jeopardize the safety of the subject, and may require medical or surgical intervention to prevent 1 of the outcomes listed above in this definition. Examples of such events are intensive treatment in an emergency room or at home for allergic bronchospasm, blood dyscrasia, or convulsions that do not result in hospitalization.

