### 6.3 Risk/Benefit Assessment

Metvix® cream (methyl aminolevulinate 16.8%) is currently marketed worldwide by Galderma for the treatment of thin or non-hyperkeratotic and non-pigmented AK of the face and scalp, and in some countries for the treatment of superficial and nodular BCC and the treatment of SCC *in situ* (Bowen's disease) in adults.

The cumulative post-marketing patient exposure to MAL cream is estimated to be 2,213,42 patient treatments, calculated on the basis of number of tubes sold worldwide and the assumption that a single 2-g tube is used for 2 patient treatments. In the near future, the 2-g tube will be a unidose tube, intended for one use only.

Galderma has developed a new treatment regimen of the product in which DL is used in place of the previously authorized red light-emitting diode (LED) for the illumination in the treatment of AKs. This has been approved in various countries and Galderma is now developing methyl aminolevulinic acid cream 16.8% (CD06809-41) DL-PDT in the United States for the treatment of AK.

With regards to safety, in clinical studies conducted with MAL c-PDT in subjects with AKs, BCC, or Bowen's disease, approximately 60% of subjects experienced reactions localized to the treatment site, attributable to toxic effects of the photodynamic therapy (phototoxicity) or to preparation of the lesion. The most frequent symptoms were painful and burning skin sensation, typically beginning during illumination or soon after and lasting for a few hours with resolution on the day of treatment. The symptoms were usually of mild or moderate severity and rarely required early termination of illumination. The most frequent signs of phototoxicity were erythema and scab. The majority were of mild or moderate severity and persisted for 1 to 2 weeks, or occasionally longer. Repeated treatment with Metvix was associated with a reduced frequency and severity of local phototoxic reactions.

In the post-marketing experience, the following adverse drug reactions were the more relevant ones reported with Metvix cream: eyelid edema, angioedema, face edema (swelling face), application site eczema, allergic contact dermatitis, and rash pustular (application site pustule). In addition, hypertension and transient global amnesia were reported with Metvix cream used with c-PDT (refer to the Investigators' Brochure).

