#### 9.2.4.2 Adverse Events of Special Interest (AESIs)

An AESI is a noteworthy event for the particular study drug that can be appropriate to monitor closely. It could be serious or non-serious and AESIs could include events that might be potential precursors or prodromal symptoms for more serious medical conditions in susceptible individuals.

The AESIs for this protocol have been predefined as follows:

- Contact sensitization see [Section 9.4.4](#)

At each visit, particularly Visits 3 and 5, the Investigator should examine the treatment area(s) carefully and be aware of the potential for contact irritation and contact sensitization. Contact sensitization is an AESI. For AESIs, the Investigator is required to complete the Adverse Event Form in the eCRF, within 72 hours of the event, otherwise follow the SAE reporting procedures in [Section 9.2.4.3](#), even if the event is considered non-serious according to the usual regulatory criteria.

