- Number and percentage (n, %) of subjects with any TEAE leading to study discontinuation and frequency of TEAEs leading to study discontinuation overall and by System Organ Class and Preferred Term;
- Number and percentage (n, %) of subjects with any TEAE leading to study drug discontinuation and frequency of TEAEs leading to study drug discontinuation overall and by System Organ Class and Preferred Term.

The same summaries of TEAEs will be provided for the following subgroups: baseline AK grade (Grade 1 AK and Grade 2 AK), sex (Male and Female), number of baseline AK lesions (4-8 AK lesions and 9-12 AK lesions) and Fitzpatrick skin type (Type I, II and III and Type IV, V and VI).

A summary table of TEAEs will be provided for the following in the safety population by treatment group and overall:

- Number and percentage (n, %) of subjects with any TEAE and frequency of TEAEs, that occurred in >5% of subjects of the safety population, overall and by System Organ Class and Preferred Term.

A summary table of serious TEAEs will be provided for each of the following in the safety population by treatment group and overall:

- Number and percentage (n, %) of subjects with any Serious TEAE and frequency of Serious TEAEs overall and by System Organ Class and Preferred Term;
- Number and percentage (n, %) of subjects with any Serious TEAE by closest relationship to study drug and frequency of Serious TEAEs by closest relationship to study drug overall and by System Organ Class and Preferred Term;
- Number and percentage (n, %) of subjects with any Serious TEAE by closest relationship to study procedures and frequency of Serious TEAEs by closest relationship to study procedures overall and by System Organ Class and Preferred Term;

Statistical Analysis Plan

- Number and percentage (n, %) of subjects with any Serious TEAE related to the study drug and frequency of Serious TEAEs related to the study drug by System Organ Class and Preferred Term;
- Number and percentage (n, %) of subjects with any Serious TEAE related to the study procedures and frequency of Serious TEAEs related to the study procedures by System Organ Class and Preferred Term;
- Number and percentage (n, %) of subjects with any Serious TEAE leading to study discontinuation and frequency of Serious TEAEs leading to study discontinuation overall and by System Organ Class and Preferred Term;

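### The life-threatening criterion for SAEs (Protocol 9.2.4.1) joins two opposite tests, so sites can classify the same reaction differently

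*Protocol*

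**What the plan says.** Protocol 9.2.4.1 lists the criteria that make an adverse event serious. The second is that the event is life-threatening, explained in one parenthesis. The opening clause reads "an AE is life-threatening if the subject was at immediate risk of death from the event as it occurred". From its last three words the sentence runs on: "as it occurred, i.e., it includes a reaction that might have caused death if it had occurred in a more serious form".

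The last criterion in the same list rests on medical judgment: "An important medical event that may not result in death, be life-threatening, or require hospitalization, may be considered an SAE". Its examples are allergic bronchospasm treated intensively in an emergency room or at home, blood dyscrasia, and convulsions without admission.

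Severity is graded separately (Protocol 9.2.4, Assessment of Severity). No minimum severity is set for the life-threatening criterion. SAP 6.2.4 gives no definition of life-threatening and refers the reader to the protocol for further detail on adverse events.

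Two things follow from an event being serious. The investigator must notify the safety group within 24 hours (Protocol 9.2.4.3). The event also enters the serious-TEAE summaries in SAP 10.7.3, which begin with the number and percentage of "subjects with any Serious TEAE and frequency of Serious TEAEs overall".

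**The concern.** A connective such as i.e. tells the reader that the second clause means the same as the first. Here it does not. A reaction that could have killed only in a worse form did not put the subject at immediate risk in the form it took.

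This is an operative rule, applied by investigators at about 60 sites. The reactions on which the halves disagree are relevant to this product: Protocol 6.3 names, among the more relevant post-marketing reactions, "eyelid edema, angioedema, face edema (swelling face), application site eczema, allergic contact dermatitis". Angioedema and facial swelling occur across a wide range of severity. Two careful sites could see the same limited facial swelling, and one would report an SAE while the other would not, each with support in the text. The serious-TEAE tables would then mix two definitions.

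**Working it through.** The plan gives no figure to reproduce. The check sets the two halves side by side and then tests each against the rest of the section.

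**Step 1. Where the halves agree and differ.**

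| Event, in the form observed | First half (actual event) | Second half (hypothetical worse event) |
|---|---|---|
| A. Immediate risk of death | life-threatening | life-threatening |
| B. No immediate risk, but a worse form might be fatal | not life-threatening | life-threatening |
| C. No immediate risk and no fatal form | not life-threatening | not life-threatening |

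The contradiction is confined to row B. Ordinary mild events in row C are unaffected.

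**Step 2. Does severity grading close the gap?** No. A mild event is defined as "An AE that is easily tolerated by the subject, causes minimal discomfort, and does not interfere with everyday activities". A reaction can meet that description and still sit in row B, because nothing in the second half refers to the severity actually observed.

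**Step 3. Which half fits the rest of 9.2.4.1?** The judgment-based criterion covers events that may not be life-threatening. Its examples, bronchospasm and convulsions among them, could be fatal in a worse form, so they belong in row B. Under the first half they are not automatically life-threatening, and the criterion has work to do. Under the second half they are already life-threatening and therefore already serious, which leaves that criterion little to cover. The structure of the section fits only the first half.

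**Step 4. Does another section settle it?** No. Neither document defines life-threatening elsewhere, and the SAP points back to the protocol.

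**Step 5. What depends on it.** SAP 10.7.3 plans eight serious-TEAE summaries: overall; by closest relationship to drug; by closest relationship to procedures; drug-related; procedure-related; leading to study discontinuation; leading to drug discontinuation; leading to death. It adds a COVID-19 serious-TEAE table and a listing of serious AEs. Protocol 8.3.4 also lets the sponsor end the study in case of SAEs.

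**Step 6. Size.** The number of added SAEs is the number of row B events not serious on another criterion, multiplied by the share of them classified under the second half. The documents give neither quantity, nor any SAE rate. All that can be computed is the weight of one subject, taking the planned arm sizes as the safety population: 1/380 = 0.26 percentage points in the MAL arm and 1/190 = 0.53 in the vehicle arm.

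**The case against.** The best defense is that investigators will read the sentence in context. Immediate risk from the actual event is the governing condition and the rest is a clumsy gloss. The bronchospasm example points the same way. Staff are trained on ICH/GCP (Protocol 11.3), and 9.2.4.2 mentions events handled under the SAE route "even if the event is considered non-serious according to the usual regulatory criteria", which suggests conventional criteria are intended. This lowers the chance of the literal reading, but attendance at the training meeting is only recommended, and none of it corrects the text.

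The defense does succeed against several stronger inferences a reader might draw:

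- **That 9.2.4.1 also conflicts with the AESI section.** It does not. Section 9.2.4.2 says an AESI may be serious or non-serious, which is compatible with either half.
- **That mild reactions in general become SAEs.** Only row B is affected, and only on a literal reading. Urticaria is not among the reactions listed in 6.3, and hypertension is tied there to conventional PDT.
- **That serious TEAEs will be inflated in the MAL arm.** The documents do not show this. Vehicle subjects undergo the same sunscreen, curettage and daylight exposure, and the protocol anticipates hypersensitivity to excipients. Sites are blinded and randomization is stratified by center, so differing site readings do not in themselves favor an arm.
- **That the serious-TEAE rate would be unreadable.** Severity is recorded separately and all serious AEs are listed, so a mild event marked serious could be found. Safety analysis is descriptive (SAP 10.7), and over-reporting does not hide harm.

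**Conclusion.** The criterion is wrong as written. Its two halves are opposite tests, no other text reconciles them, and the last criterion in the same list is coherent only with the first half. Read literally, the second half can turn a non-dangerous form of a reaction with a fatal extreme into an SAE, and sites can diverge while following the protocol.

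The effect is limited to the consistency of seriousness classification, expedited reporting and the descriptive serious-TEAE tables. It runs toward over-reporting. Neither its size nor any imbalance between arms can be estimated from the documents. The efficacy endpoints, alpha of 0.00125, power and sample size are not affected. The conclusion about the wording rests on the protocol's own sentence. The conclusion about consequences assumes that at least some investigators would apply the second half literally, which the documents neither show nor exclude.

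**What to change.** In Protocol 9.2.4.1, replace the clause after i.e. so that both halves state the same test. For example: *a reaction that did not endanger life in the form observed is not covered, even if a worse form of it could have been fatal.* Tell sites of the change in a short memo.

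Reviewing events already reported as life-threatening is optional and needs safeguards. It should be blinded to treatment, finished before database lock, and keep the original classification in the audit trail, because such a review can only downgrade events. It may not be fully feasible: the data listed for each AE in Protocol 9.2.4 include serious or not serious, but not the criterion that was met.

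The cost is one protocol wording change and a site memo, with slightly fewer events classed as serious. No new data are needed. All adverse events are still recorded, and the judgment-based criterion still captures non-fatal events that put the subject in jeopardy.

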#### 9.2.4.2 Adverse Events of Special Interest (AESIs)

An AESI is a noteworthy event for the particular study drug that can be appropriate to monitor closely. It could be serious or non-serious and AESIs could include events that might be potential precursors or prodromal symptoms for more serious medical conditions in susceptible individuals.

The AESIs for this protocol have been predefined as follows:

- Contact sensitization see [Section 9.4.4](#)

At each visit, particularly Visits 3 and 5, the Investigator should examine the treatment area(s) carefully and be aware of the potential for contact irritation and contact sensitization. Contact sensitization is an AESI. For AESIs, the Investigator is required to complete the Adverse Event Form in the eCRF, within 72 hours of the event, otherwise follow the SAE reporting procedures in [Section 9.2.4.3](#), even if the event is considered non-serious according to the usual regulatory criteria.

